NC ProCESS is a population-based cohort designed specifically to address well-described knowledge gaps. It was designed in close collaboration with the unique AHRQ consortium stakeholder group, which included representatives from patients, clinicians and policymakers. Stakeholders helped define study design to emphasize "real-world" patients and select patient-centered and relevant outcomes, and have been involved throughout assembly of this patient cohort. The diverse cohort is well-represented by "hard to reach" patients; enrollment before treatment avoids biases with participation and recall. As clinical trials are not feasible to address the central questions in prostate cancer CER, this prospective study will yield the

highest level of evidence to inform patients and other stakeholders. With an assembled cohort, this study is necessary to examine comparative outcomes.

Study Design:

Study Type:	Observational
Actual Enrollment:	1656 participants
Observational Model:	Cohort
Time Perspective:	Prospective
Study Start Date:	January 2011
Estimated Primary Completion Date:	December 2018
Estimated Study Completion Date:	December 2018

Outcome Measures:

Primary Outcome Measure:

1. Patient Reported Outcomes [Time Frame: 4 years]
Directly compare patient-reported prostate-cancer specific and global quality of life (QOL), anxiety regarding prostate cancer and decisional regret in a cohort of men with localized prostate cancer managed by active surveillance, radical prostatectomy, radiation therapy, and brachytherapy.
2. Disease-Free Survival [Time Frame: 5 years]
Directly compare the disease-free survival among different treatment options for prostate cancer.
3. Directly compare health care utilization among different treatment options for prostate cancer from review of medical records [Time Frame: 4 years]
For each treatment group (radiation therapy, prostatectomy, active surveillance), we will describe the cumulative utilization for each category of health care. These categories are physician/specialty visits, hospitalizations, diagnostic tests/procedures, medications, and prostate cancer treatments (for the initial cancer and for recurrence).
Measurements will be attained by review of medical records.

Eligibility Criteria:

Ages Eligible for Study:	35 Years to 80 Years
Sexes Eligible for Study:	Male

Accepts Healthy Volunteers: No
Sampling Method: Non-Probability Sample

Study Population

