Newly-diagnosed, early stage (localized, non-metastatic) prostate cancer patients

Inclusion Criteria:

- Newly-diagnosed, histologically-proven, localized prostate adenocarcinoma.
- Completion of baseline interview prior to initiating therapy.
- Patient ability to complete study interview: no cognitive impairment, language or hearing problems.
- Not diagnosed with prostate cancer through transurethral resection of the prostate (TURP).
- Age 35-80.
- English speaking.
- Has telephone.

Exclusion Criteria:

- Initiation of treatment for prostate cancer prior to completion of baseline interview.
- Cognitive impairment.
- Hearing problems.
- Inability to speak or understand English.

Analytical and Statistical Approaches

Aim 1: Consistent with the prostate cancer QOL literature, we treated each patient-reported outcome measure as a continuous variable. We described the mean, standard deviation, and range of each measure at each time point, as well as the change from each time point compared to the baseline measure. Differences among treatment groups were compared using t-tests. A unique aspect of the PCSI instrument is that scores in each domain (Urinary Incontinence, Urinary Obstruction/Irritation, Bowel Problems, Sexual Dysfunction) are translatable into functional categories: normal, intermediate, and poor.^{2,37} Thus, we explored QOL measures using functional categories to facilitate creation of patient-friendly dissemination materials that summarize study findings. Further, to examine differences in outcomes across treatments, we conducted linear regression models applying propensity scores; a separate model was constructed for each outcome measure. We used generalized estimating equations (GEE) to account for correlation of the outcome measured repeatedly over time. In addition, we included time as a categorical variable and added a time*treatment interaction in the models to account for a non-linear change in outcome over time.

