4. **Handling of missing data:** We followed the PCORI standards for handling and minimizing the impact of missing data. First, we carefully examined the pattern of missing data by individual items. We determined whether the missing data is informative, missing not at random (MNAR), missing completely at random (MCAR), or missing at random (MAR) by evaluating patient characteristics (e.g., age, race and ethnicity, treatment). We also compared those patients with missing data to patients with complete data. We then imputed missing data using a widely-employed multiple imputation approach.⁶¹ This method replaces the missing data with a set of m possible values by creating m imputed datasets through Monte Carlo technique. Each imputed dataset was analyzed using the same methods that are used for complete datasets. Results were pooled together to provide valid statistical inferences.⁶¹ These methods enabled us to use data from the entire study sample, including patients with differential follow-up, maximizing the study’s statistical power to detect differences among

treatment groups. Lastly, we conducted sensitivity analyses to examine the impact of the missing data on study results.^{62–65}

5. **Cluster analysis:** We examined for possible clustering within our study sample as data may have been clustered at several levels. For example, patients treated by the same physicians or facilities may have correlated outcomes, and patients living in the same area may share characteristics related to treatment outcomes. To account for clustering in our analysis of DFS (Aim 2), we conducted proportional hazard model using a robust sandwich estimate⁶⁶ and likelihood-based random effect (frailty) model.⁶⁷ For outcomes analyzed by linear and logistic regression models, we used GEE modeling approaches to obtain appropriate standard errors, and/or applied multilevel modeling to explicitly model the clustered data structures and allow for random intercepts of the higher level data structure.

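### Does the claim to have determined the missing-data mechanism from patient characteristics undermine the patient-reported comparisons?

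*Combined protocol and SAP*

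**What the plan says.** The relevant text is item 4 (Handling of missing data) under Bias and Confounding. After looking at missingness item by item, the authors write "We determined whether the missing data is informative, missing not at random (MNAR), missing completely at random (MCAR), or missing at random (MAR", and the stated basis is "by evaluating patient characteristics (e.g., age, race and ethnicity, treatment". They also compared men with and without missing data. Then: "We then imputed missing data using a widely-employed multiple imputation approach". The number of imputations is left as m, and pooling is said to give valid inference, with no condition on the mechanism. The benefit claimed is this: "These methods enabled us to use data from the entire study sample, including patients with differential follow-up". The item closes: "Lastly, we conducted sensitivity analyses to examine the impact of the missing data on study results", with references but no description.

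Two other places bear on the point. The Inclusion Criteria require "Completion of baseline interview prior to initiating therapy", so every man should have a baseline interview. Aim 1, under Analytical and Statistical Approaches, uses GEE "to account for correlation of the outcome measured repeatedly over time", so earlier scores exist for many men whose later score is missing. Patient-reported outcomes are the first primary outcome listed, with a 4-year time frame.

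**The concern.** MAR and MNAR differ only in whether, given what was observed, missingness still depends on the unseen value. Age, race, treatment and a comparison of incomplete with complete cases all use observed data. They can show that missingness is not completely at random; they cannot show which of the other two holds. So the stated determination is not available from the stated method.

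The imputation is what brings men with incomplete follow-up into the 4-year comparisons. Suppose men with poor current function respond less often than their earlier scores would predict, and the rate or the mechanism differs by treatment. A standard imputation would then flatter one group, while the check described would look just as it does under MAR. A reader cannot tell from the text whether the reported sensitivity analyses cover that case.

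**Working it through.** The plan states no missing-data rate, SD, correlation or important difference, so it has no figure to reproduce. The check has three parts.

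**1. Can the described check separate MAR from MNAR?** Let the outcome Y depend on an observed covariate X, and let the unseen Y be shifted by delta given X. Delta does not enter the distribution of anything observed. A simulation (200 × 1656 records, slope 0.5, missingness logistic in X, about 21% missing) gave:

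| | delta = 0 (MAR) | delta = −0.5 SD (MNAR) |
|---|---|---|
| X, observed minus missing | 0.481 | 0.481 |
| Mean of observed Y | 0.050 | 0.050 |
| Slope of Y on X | 0.498 | 0.498 |
| Imputed mean | 0.00 | 0.00 |
| True mean | 0.00 | −0.105 |

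The last entry is 0.21 × (−0.5) = −0.105. The two cases look identical in the data, so the criticism of the verb is correct.

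**2. Does anything in the plan turn on the classification?** Item 4 runs in this order: examine patterns, classify, compare, impute, pool, run sensitivity analyses. No verdict is reported, and no branch is described in which the verdict selects a method. Nor does the text say that the imputation would have been the same under any verdict; it is silent. The comparison keeps a proper use: evidence against MCAR, and help in choosing imputation variables. The listed characteristics are given as examples and include treatment, so the list is not exhaustive.

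**3. How large could the bias be?** All inputs here are assumed. Bias in a group mean = missing fraction × shift of the missing men from their imputed prediction. Bias in a contrast = difference of these products between two groups. Shifts come from a simulation of 3,000,000 men per group, with missingness logistic in the outcome and slopes set so that men with missing data are 0.37 to 0.39 SD lower on the earlier score, as in the MAR comparator.

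| Missing | Mechanism | Correlation 0.7, shift 0.28 | Correlation 0.8, shift 0.17 |
|---|---|---|---|
| 10% vs 30% | MNAR in both | 0.20 × 0.28 = 0.056 | 0.20 × 0.17 = 0.034 (simulated 0.035) |
| 10% vs 20% | MNAR in both | 0.10 × 0.28 = 0.028 | 0.10 × 0.17 = 0.017 (simulated 0.018) |
| 20% vs 20% | same in both | 0.000 | 0.000 |
| 20% vs 20% | MAR in one, MNAR in the other | 0.20 × 0.28 = 0.056 | 0.20 × 0.17 = 0.034 |

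With two earlier scores in the imputation model the shifts fall to 0.24 and 0.14. At 10% vs 30% that gives 0.20 × 0.24 = 0.048 (simulated 0.047) and 0.20 × 0.14 = 0.028.

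For scale, take four equal groups (four treatments are named in Primary Outcome Measure 1; equal size is assumed): 1656/4 = 414 per group, and the standard error of an unadjusted difference is √(2/414) = 0.07 SD. The non-zero one-score biases of 0.018 to 0.056 SD are 0.26 to 0.81 of that. At 0.81 standard errors a nominal 95% interval covers about Φ(1.96 − 0.81) − Φ(−1.96 − 0.81) = 0.87.

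The range depends on the correlation. At 0.5 the shift is 0.56 to 0.58 SD, and 10% vs 30% gives 0.20 × 0.56 = 0.11 to 0.20 × 0.58 = 0.12 SD, more than one such standard error. The standard error is also not that of the planned weighted, trimmed GEE analysis.

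**The case for a change.** The strongest case for a change is that the sentence claims something impossible by definition, that pooled inference is then called valid without any condition, and that the outcomes affected are primary. The remedy would be cheap: name the assumption, list the imputation variables, and describe or add an analysis that departs from MAR. Reading the verb loosely does not fill in the assumption or the sensitivity analyses.

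Much of this stands. The verb overstates what the check can deliver, and the details are not in the text. What does not follow is that the analysis is deficient. The text does not show that baseline or earlier scores were left out of the imputation, or that the sensitivity analyses all kept to MAR. Their cited sources cannot be consulted here, and silence in a short past-tense summary does not count against work reported as done. A delta-adjusted imputation with a tipping point is one acceptable way to probe MNAR among several, and asking for it presumes that nothing equivalent was done.

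**Conclusion.** No change to the plan is needed. This is loose wording plus a gap that analysts fill sensibly. Anyone running a standard multiple imputation on these data would treat MAR, given covariates, treatment and earlier scores, as a working assumption, and would use the sensitivity analyses to ask how far the results depend on it. The steps reported are consistent with that, and no result is shown to rest on the claimed classification.

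The possible size is unknown. Under assumed correlations of 0.7 to 0.8 the contrast biases run from zero to 0.056 SD, below one assumed standard error, and would matter mainly for small or near-null contrasts. A correlation of 0.5 would take the bias to about 0.11 SD. The conclusion assumes that earlier scores entered the imputation and that the sensitivity analyses tested the missing-data assumption; the text neither confirms nor contradicts either. Evidence that both failed, alongside markedly unequal missingness between treatments, would reopen the question for the patient-reported outcomes.
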